## LIST OF ABBREVIATIONS AND DEFINITION OF TERMS

Abbreviations and Definition of Terms	
δ	Delta
Ab	Antibody
ADCC	Antibody-Dependent Cellular Cytotoxicity
AE	Adverse Event
ALP	Alkaline Phosphatase
ALT	Alanine aminotransferase
AST	Aspartate aminotransferase
ATC	Anatomic Therapeutic Class
AUC	Area Under the Curve
BM	Bone Marrow
Ca	Calcium
CBC	Complete Blood cell Count
CD	Cluster of Differentiation
CDC	Complement-Dependent Cytotoxicity
Cl	Clearance
CLL	Chronic Lymphocytic Leukemia
Cmax	Maximum Concentration
CMV	Cytomegalovirus
CR	Complete Response
CRF	Case Report Form
CRO	Contract Research Organization
CTCAE	Common Terminology Criteria for Adverse Events
CV	Curriculum Vitae
D, d	Day
DLBCL	Diffuse large B-cell lymphoma
DLT	Dose Limiting Toxicity
DOR	Duration of Response
DRG	Data Review Group
DVT	Deep Vein Thrombosis
EC	Ethics Committee
ECG	Electrocardiogram
ECOG	Eastern Cooperative Oncology Group
Fc	Fragment crystallizable (region)
FL	Follicular Lymphoma
FU	Follow-up
GCP	Good Clinical Practice
HBV	Hepatitis B Virus
HCV	Hepatitis C Virus
IEC/IRB	Independent Ethics Committee (IEC) or Institutional Review Board (IRB)
Ig	Immunoglobulin
ICH	International Conference on Harmonisation of Technical Requirements for Registration of Pharmaceuticals for Human Use
IRR	Infusion-related reaction
IV	Intravenous
LDH	Lactate dehydrogenase

Abbreviations and Definition of Terms	
MCL	Mantle Cell Lymphoma
MRD	Minimal Residual Disease
MRT	Mean Residence Time
MZL	Marginal Zone Lymphoma
mAb	Monoclonal Antibody
MedDRA	Medical Dictionary for Regulatory Activities
NCI-WG	National Cancer Institute – Working Group
NK	Natural Killer
NHL	Non-Hodgkin’s Lymphoma
NYHA	New York Heart Association
ORR	Overall response rate
OS	Overall survival
PI3K	Phosphoinositide-3-kinase
PCD	Programmed cell death
PFS	Progression-Free Survival
PD	Pharmacodynamic or Progressive Disease
PK	Pharmacokinetic
PPS	Per Protocol Set
PR	Partial Response
PT	Preferred Term
R-FC	Rituximab-Fludarabine, Cyclophosphamide
SAE	Serious Adverse Event
SAP	Statistical Analysis Plan
SD	Stable Disease
SLL	Small lymphocytic leukemia
SOC	System Organ Class
t1/2	Half-Life of Elimination
ULN	Upper limit of normal
UTX, TG-1101	Ublituximab
V	Visit
Vd	Volume of distribution
WHO	World Health Organization
WM	Waldenström’s Macroglobulinemia

## 1 INTRODUCTION

---

### 1.1 CHRONIC LYMPHOCYTIC LEUKEMIA

---

In the US, an estimated 15,720 new cases of Chronic Lymphocytic Leukemia (CLL) will be reported in 2014 with deaths totaling 4,600 due to the disease according to American Cancer Society estimates (American Cancer Society, 2014). CLL affects mainly older adults, accounts for one third of all diagnosed cases of leukemia and is characterized by the accumulation of clonal mature B lymphocytes in the blood, bone marrow, and secondary lymphoid tissues (Lin K, 2002). CLL is a heterogeneous disease, with several higher risk cytogenetic abnormalities which are generally more difficult to treat, including 17p deletion, P53 gene mutation, and 11q deletion (Hallek M, 2008) (Lin K, 2002). Subjects with 17p deletion show higher resistance to conventional chemotherapies as well as shorter duration of survival than non 17p deletion subjects. Subjects with 11q deletion have been associated with marked lymphadenopathy (Hallek M, 2008). Subjects with P53 gene mutations are associated with an adverse clinical outcome (Lin 2002).

Chemotherapy regimens in combination with monoclonal antibody therapy comprise the current standard of care for subjects with CLL, with novel targeted agents now entering the market. Frontline therapy for subjects with CLL generally consists of the anti-CD20 monoclonal antibody rituximab, in combination with either fludarabine and cyclophosphamide, or bendamustine. Depending on the age and comorbidities of the subject, chlorambucil is also considered, though its use within the US has been limited. Other anti-CD20 antibodies have also been approved for the treatment of CLL, including ofatumumab and obinutuzumab. Recently the BTK inhibitor, ibrutinib was approved by the FDA for the treatment of subjects with CLL in the relapsed or refractory setting after demonstrating superiority to ofatumumab as measured by progression free survival (Byrd et al, 2014). Despite these advancements in available therapies, CLL remains an incurable disease, and many subjects will progress and eventually die from their disease. Furthermore, subjects with higher risk cytogenetic abnormalities still present with a less than optimal response to approved therapies and shorter duration of response and progression free survival. As such, there is a pressing need for new, innovative, targeted therapies for the treatment of subjects with relapsed/refractory CLL, especially those with cytogenetic abnormalities.

### 1.2 BACKGROUND

---

A Phase 3 randomized study (UTX-TGR-304) to assess the efficacy and safety of ublituximab in combination with TGR-1202 compared to obinutuzumab in combination with chlorambucil in subjects with chronic lymphocytic leukemia (CLL) was launched in September 2015. As part of the study design, subjects from Treatment Arms B, C, and D with disease progression confirmed by the independent review committee (IRC), may be enrolled into this companion study. In addition, at the end of the UTX-TGR-304 study, non-progressed subjects from all treatment arms may also be enrolled to this companion study.

### 1.3 UBLITUXIMAB

---

Ublituximab is a novel third generation chimeric anti-CD20 monoclonal antibody bioengineered for potent activity, exhibiting a unique glycosylation profile with a low fucose content, designed to

introduce superior antibody-dependent cytotoxicity (ADCC). Ublituximab has maintained competitive complement-dependent cytotoxicity (CDC) and has also demonstrated to induce programmed cell death (PCD) upon binding to the CD20 antigen on B-lymphocytes. Ublituximab has a unique protein sequence, and targets epitopes on CD20 not targeted by rituximab or ofatumumab, both currently approved anti-CD20 antibodies.

#### 1.4 TGR-1202 (UMBRALISIB)

TGR-1202 is a highly specific and orally available phosphoinositide-3-kinase (PI3K) delta ( $\delta$ ) inhibitor with nanomolar inhibitory potency, and high selectivity over the alpha, beta, and gamma isoforms. The PI3Ks are a family of enzymes involved in various cellular functions, including cell proliferation and survival, cell differentiation, intracellular trafficking and immunity. The delta isoform of PI3K is highly expressed in cells of hematopoietic origin, and strongly upregulated, and often mutated in various hematologic malignancies. TGR-1202 has demonstrated safety in ongoing Phase I, II, and III clinical trials in subjects with hematologic malignancies and solid tumors. TGR-1202 is manufactured by Alembic Pharmaceuticals and supplied by TG Therapeutics, Inc.

#### 1.5 UBLITUXIMAB IN COMBINATION WITH TGR-1202

The combination of ublituximab and TGR-1202 is currently under evaluation in an ongoing Phase I/Ib study in subjects with relapsed or refractory NHL and CLL ([Lunning et al., ASH 2015](#)). In this study, ublituximab is being dosed on Days 1, 8, and 15 of Cycle 1 & 2, and on Day 1 of Cycles 4, 6, 9 and 12. After Cycle 12, no further ublituximab is administered and TGR-1202 is continued until removal from study.

A 3+3 dose-escalation design is being utilized to evaluate sequentially higher doses of the combination agents as illustrated below:

Cohort	Ublituximab NHL Dose	Ublituximab CLL Dose	TGR -1202 Dose (QD)
1	900 mg	600 mg	800 mg
2	900 mg	600 mg	1200 mg
3	900 mg	900 mg	400 mg (micronized)
4	900 mg	900 mg	600 mg (micronized)
5	900 mg	900 mg	800 mg (micronized)
6	900 mg	900 mg	1200 mg (micronized)

As of December 1, 2014, 27 subjects have been enrolled and are evaluable for safety, with 26 subjects evaluable for efficacy. The median age was 65 years (range 35 – 82), 17 Male/10 Female, with histologies as follows: 10 CLL/SLL, 9 FL, 7 DLBCL, and 1 subject with Richter's Transformation. Subjects had a median of 3 prior therapies, and 41% were refractory to prior therapy.

Among the 27 subjects evaluable for safety, Infusion Related Reaction (IRR) was the most prevalent adverse event (52%), followed by neutropenia (41%), nausea (37%), diarrhea (33%), fatigue (30%), and insomnia (30%). Adverse events were observed to be similar across dosing cohorts, and only one subject had their dose of TGR-1202 reduced (Gr. 1 diarrhea). IRR and neutropenia were managed through dose delays, with 1 CLL subject having a neutropenia related dose delay which met the criteria for a DLT, necessitating enrollment of additional CLL subjects into Cohort 1. One subject

was removed from study without progressive disease due to an event of itching which was deemed possibly related to TGR-1202.

Subjects were heavily pretreated, and amongst subjects with DLBCL and CLL, contained numerous high-risk subjects (67% of CLL subjects had 17p del and/or 11q del, and 5/7 evaluable DLBCL subjects were of Germinal Center-B-Cell subtype).

Responses are as follows:

- All 9 CLL/SLL subjects showed significant nodal reductions with 6 (67%) achieving a PR per iwCLL criteria (Hallek 2008). Additionally, all CLL subjects achieved a greater than 50% reduction in ALC by the end of Cycle 3.
- All 9 evaluable FL subjects displayed a nodal reduction on the combination, with 2 subjects achieving a response per Cheson 2007 criteria, including one subject with a PET negative complete response.
- Of the 7 evaluable DLBCL subjects, 3 (43%) achieved a response, including 2 complete responses which were confirmed by independent radiologic review.
- The 1 subject with Richter's Transformation exhibited a 49% nodal reduction and remains on study (duration as of data cutoff of 7+ months)

Overall, the preliminary data suggests the combination of ublituximab and TGR-1202 is well tolerated and active in subjects with relapsed or refractory hematologic malignancies, including those with CLL (both high and low risk).

## 2 OBJECTIVES

---

### 2.1 STUDY OBJECTIVES

---

#### **Primary Objectives**

- To observe the overall response rate (ORR) defined as the sum of complete responses (CR) and partial responses (PR)

#### **Secondary Objective**

- To observe progression-free survival (PFS) and duration of response (DOR)
- To observe the % of subjects that achieve MRD negativity
- To observe the safety of ublituximab in combination with TGR-1202

### 2.2 EFFICACY ENDPOINTS

---

#### **Overall response rate (ORR)**

ORR is defined as sum of CR and PR rates.

#### **Complete Response (CR) Rate**

CR rate is defined as the proportion of subjects who achieve a CR.

#### **Progression-free survival (PFS)**

PFS is defined as the interval from randomization to the earlier of the first documentation of definitive disease progression or death from any cause.

Definitive disease progression based on standard criteria ([Hallek et al. 2008](#)) and occurring for any reason (i.e., increasing lymphadenopathy, organomegaly or bone marrow involvement; decreasing platelet count, hemoglobin, or neutrophil count; or worsening of disease-related symptoms) other than lymphocytosis.

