Efficacy Endpoints	
Overall response rate (ORR) ORR is defined as sum of CR and PR rates.
 
Complete Response (CR) Rate CR rate is defined as the proportion of subjects who achieve a CR.
 
Progression-free survival (PFS) PFS is defined as the interval from enrollment to the earlier of the first documentation of definitive disease progression or death from any cause. Definitive disease progression based on standard criteria (Hallek et al. 2008) and occurring for any reason (i.e., increasing lymphadenopathy, organomegaly or bone marrow involvement; decreasing platelet count, hemoglobin, or neutrophil count; or worsening of disease-related symptoms) other than lymphocytosis.
 
Minimal Residual Disease (MRD) Negativity Rate MRD negativity rate is defined as the proportion of subjects who are MRD negative.
 
Duration of response (DOR) DOR is defined as the interval from the first documentation of CR or PR to the earlier of the first documentation of definitive disease progression or death from any cause.

Safety Endpoints	All AEs will be reported and evaluated using National Cancer Institute's Common Terminology Criteria (CTCAE) v4.0.
Study Design	
This study is intended to serve as a compassionate use study to allow subjects who have previously progressed on Arms B, C & D in the parent trial UTX-TGR-304 to receive ublituximab plus TGR-1202. Those subjects must have had confirmed disease progression by the independent radiology committee (IRC). Additionally, at the termination of study UTX-TGR-304, non-progressed subjects from Treatment Arm A may be enrolled to this study.
 
Subjects from Treatment Arms B, C, and D may start treatment with ublituximab + TGR-1202, while subjects entering this study from Treatment Arm A may continue their treatment until they show disease progression, are unable to continue treatment for any reason such as lack of tolerability, or until the treatment is commercially available.

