### 3.1 INCLUSION CRITERIA

---

1. Prior treatment in clinical trial [UTX-TGR-304](#)
  - a. Confirmed progression by IRC on Arms B, C, or D after at least two cycles of treatment in trial UTX-TGR-304. There is no required timeframe to begin treatment on the UTX-TGR-204 protocol; however, if other therapies to treat the disease are implemented in the interim, the subject will not be eligible to enroll in the study.
  - b. Non-progressing subjects on Arm A may be eligible for enrollment when protocol UTX-TGR-304 is completed.
2. Adequate organ system function, defined as follows:
  - a. Absolute neutrophil count (ANC)  $> 750 \times 10^3/\text{mm}^3$  (0.75 K/ $\mu\text{L}$ ) / platelet count  $> 40 \times 10^3/\text{mm}^3$  (40 K/ $\mu\text{L}$ ) unless cytopenias are related to bone marrow involvement.
  - b. Total bilirubin  $\leq 1.5$  times the upper limit of normal (ULN) with the exception of Gilbert's Disease and Autoimmune Hemolytic Anemia.
  - c. Alanine aminotransferase (ALT) and aspartate aminotransferase (AST)  $\leq 2.5 \times$  ULN if no liver involvement or  $\leq 5 \times$  the ULN if known liver involvement
  - d. Calculated creatinine clearance  $> 30$  mL/min (as calculated by the modified Cockcroft-Gault formula).
3. ECOG performance status  $\leq 2$
4. Ability to swallow and retain oral medication
5. Willingness and ability to comply with trial and follow-up procedures, give written informed consent

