### 4.2 REGISTRATION

---

Subjects who are eligible and who have signed an informed consent will be enrolled. Please see Study Manual for enrollment procedures.

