## 9.8.2 SECONDARY EFFICACY VARIABLES

---

Progression free survival (PFS) is defined as the time from study entry to the first documentation of tumor progression or death due to any cause whichever comes first. For subjects previously on Arm A of Study UTX-TGR-304, PFS will be calculated from the date of randomization on Study UTX-TGR-304 to the first documentation of tumor progression or death due to any cause whichever comes first. This variable will be analyzed via Kaplan-Meier methodology. The median PFS will be estimated by treatment group, if appropriate (i.e., if sample sizes are sufficient) and overall.

MRD negativity rate is defined as the proportion of subjects who are MRD negative. This variable will be analyzed by the total number and percentage of subjects who are confirmed to achieve MRD negativity as per laboratory confirmation by treatment group and overall.

Duration of response is defined as the time from documentation of a response to treatment to the first documentation of tumor progression or death due to any cause whichever comes first. For subjects previously on Arm A of Study UTX-TGR-304, unless the subject's best overall response during study UTX-TGR-304 was stable disease, the duration of response will be determined from the first documented response on Study UTX-TGR-304. Duration of the response will be summarized using n (sample size), mean, standard deviation, median, minimum and maximum for the responders by treatment group and overall.

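### Section 2.2 starts PFS at a randomization that Study 204 does not have; the Synopsis and Section 9.8.2 disagree on Arm A's origin, and the overall median mixes origins

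*Combined protocol and SAP*

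**What the plan says.** Three current parts of the combined document define PFS.

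- Synopsis, Efficacy Endpoints, with no distinction by arm: "PFS is defined as the interval from enrollment to the earlier of the first documentation of definitive disease progression or death from any cause".
- Section 2.2, also with no distinction by arm: "PFS is defined as the interval from randomization to the earlier of the first documentation of definitive disease progression or death from any cause".
- Section 9.8.2, general rule: "Progression free survival (PFS) is defined as the time from study entry to the first documentation of tumor progression". For subjects from Arm A it adds an exception: "PFS will be calculated from the date of randomization on Study UTX-TGR-304". It then asks for Kaplan-Meier medians by 304 treatment group where sample size allows, and overall.

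Entry to Study 204 is by enrollment. Section 4.2 states: "Subjects who are eligible and who have signed an informed consent will be enrolled". The randomized study is the parent, which Section 1.2 describes as "A Phase 3 randomized study (UTX-TGR-304) to assess the efficacy and safety of ublituximab". Inclusion criterion 1a in Section 3.1 admits subjects from the other three arms on this condition: "Confirmed progression by IRC on Arms B, C, or D after at least two cycles of treatment in trial UTX-TGR-304". Criterion 1b admits Arm A subjects only if they have not progressed.

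The Synopsis makes PFS a secondary objective for Arms B, C and D and a primary objective for Arm A. Section 2.1 lists a single set of objectives, which matches the Synopsis set for Arms B, C and D.

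**The concern.** A time-to-event endpoint needs an origin that exists for every subject and comes before the events it is meant to capture. The Section 2.2 origin fails this for Arms B, C and D. Their only randomization was in Study 304, and a documented progression already lies between that date and their first dose in Study 204. Applied as worded, the rule returns the outcome of the previous treatment. If an analyst avoids this by ignoring the 304 event but keeping the 304 origin, time spent on the failed treatment is credited to the combination.

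For Arm A the difficulty is different. The Synopsis and Section 9.8.2 start the clock at dates separated by the subject's whole time from 304 randomization to 204 entry, and PFS is a primary objective there. With no hypothesis test, the reported median is itself the result, so its origin has to be unambiguous.

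**Working it through.** The plan states no PFS median, event count or power, so there is no figure to reproduce. The check is a comparison of the definitions, followed by the size of the shift.

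**1. Origins side by side**

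| Source | Arms B, C, D | Arm A |
|---|---|---|
| Synopsis | enrollment | enrollment |
| Section 2.2 | randomization | randomization |
| Section 9.8.2 | study entry | 304 randomization |

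For Arms B, C and D, the Synopsis and Section 9.8.2 agree in substance and Section 2.2 is the outlier. For Arm A, Sections 2.2 and 9.8.2 agree, if randomization is taken to mean that of Study 304, and the Synopsis is the outlier.

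**2. Section 2.2 read literally, Arms B, C and D**

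The order of dates is: 304 randomization, IRC-confirmed 304 progression, 204 enrollment, any progression on 204. The first documented progression after the origin is the second item. Every subject then has the event before entering 204, nobody is censored, and 204 treatment cannot change the estimate.

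**3. Alternative reading: 304 origin, 304 event skipped**

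Reported time = (304 randomization to 204 entry) + (204 entry to 204 progression or death).

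The first term is the inflation. Inputs are at least two cycles on 304 (criterion 1a) and 28 days per cycle (stated in the Synopsis for 204; assumed here for 304).

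- Minimum: 2 × 28 = 56 days; 56 / 30.4375 = 1.84 months.
- Maximum: not limited by the plan. Criterion 1a sets no timeframe for starting 204, provided no other therapy for the disease is given meanwhile.

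**4. Illustration with assumed values**

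The documents give none of these inputs. Assume time to 304 progression is 56 days plus an exponential time, with an overall median of 6, 12 or 24 months; 204 PFS is exponential with a median of 6, 12 or 24 months; and the gap is 0 or 3 months. Simulation with 400,000 draws per setting gives:

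- Literal reading: the median equals the assumed 304 median, whatever the 204 PFS is.
- Origin at 204 enrollment: the median equals the assumed 204 PFS, apart from simulation error.
- Alternative reading, both medians 12 months: 28.7 months with no gap and 31.7 with a 3-month gap, against 12.0 from enrollment. Over the whole grid it runs from 14.0 to 60.6 months.

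**5. Arm A and the overall median**

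Arm A subjects enter 204 only if non-progressing (criterion 1b; exclusion criterion 2 removes those progressing on Arm A). Counted from 304 randomization, all their time up to 204 entry is event-free by selection. Arms B, C and D carry no such period under Section 9.8.2. The overall median therefore pools times with different origins, one of them containing a guaranteed event-free stretch.

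**The case against.** The strongest reply is that Section 9 is where the analysis methods are set, and Section 9.8.2 is workable. Its exception for Arm A would be pointless if the other arms also started at 304 randomization, so an analyst following it would not compute 304 PFS for Arms B, C and D. Section 8 also has the treating investigator determine response and progression, and Table 2 states that there is no central radiology review, so an IRC-confirmed 304 event does not look like a 204 endpoint. On this view Section 2.2 contains one stray word in a descriptive secondary endpoint.

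Most of this stands. A reader might infer that the trial will report 304 progression times as 204 PFS; read as a whole, the documents do not support that. A reader might also count three competing origins for Arms B, C and D, but enrollment and study entry are the same in substance. Nor are 56 days added unconditionally: under the literal reading nothing is added, because the interval ends at the 304 event. Adding an assumed 304 median to an assumed 204 median to get an expected reported median is not sound either. Medians do not add: 12 and 12 gave 28.7 in the illustration, not 24.

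Two things remain. Section 9.8.2 shows that Section 2.2 is mistaken but does not correct it, and no text says which section governs. The reply also leaves untouched the Arm A conflict with the Synopsis and the mixed overall median, which arises within Section 9.8.2 itself.

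One caveat: Section 1.2 says that non-progressed subjects from all arms may enter when 304 ends. The eligibility criteria offer that route only to Arm A, and the argument here follows the eligibility criteria.

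**Conclusion.** Wrong as written. The Section 2.2 origin does not exist within Study 204 and, taken from Study 304, makes the qualifying progression the PFS event for Arms B, C and D. The usable origin for those arms is already in Section 9.8.2, so this part is an error to correct rather than evidence of an intended analysis.

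The Arm A conflict carries more weight because PFS is primary there. The Synopsis and Section 9.8.2 differ by the subject's entire time from 304 randomization to 204 entry. The overall median in Section 9.8.2 has no single interpretation while the origins differ.

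On size, only the alternative reading adds time to B–D PFS: at least about 56 days per subject if 304 cycles are 28 days, with no upper limit on the gap before entry. The simulated medians rest on assumed inputs and show direction and scale only. PFS for Arms B, C and D is secondary and descriptive, and the study has no hypothesis test or powering, so alpha, power and sample size are unaffected.

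**What to change.** Use one PFS definition in the Synopsis, Section 2.2 and Section 9.8.2.

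- Arms B, C and D: start at the date of enrollment in UTX-TGR-204 and count only progression or death after that date. Say how that date relates to consent and Cycle 1 Day 1, since neither enrollment nor study entry is pinned down now.
- Arm A: state the 304-randomization origin explicitly, including in the Synopsis, and note that time up to 204 entry is event-free by selection.
- Medians: report Arm A separately and limit the pooled median to Arms B, C and D.

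The first two items are wording changes and need no new data collection for Arms B, C and D; Arm A uses a 304 randomization date that Section 9.8.2 already requires. The third changes the planned analysis in Section 9.8.2. Its cost is the loss of the all-arm overall median.
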